4.3 Treatment Regimen

PEG-IFN alfa-2a or 2b and ribavirin will be provided by each hospital and will be administered in accordance with the approved technical data sheets.

BOC (Boceprevir). Provided by the study sponsor.

Description:

BOC is supplied in 200 mg capsules. Each capsule contains 200 mg of BOC, sodium lauryl sulfate, microcrystalline cellulose, lactose monohydrate, croscarmellose sodium, pregelatinized starch, and magnesium stearate packaged in number 0 hard gelatin capsules. Each capsule contains approximately 56 mg of lactose monohydrate. In people with lactase deficiency, the clinical manifestations of lactose intolerance require 3 to 5 g of lactose (4 to 7 times the total amount of BOC capsules) to appear.

Route of administration: oral

Dosage: total daily 2400 mg, (12 capsules).

Storage: keep in the fridge at a temperature between 2°C and 8°C. The products of the study must be stored in a safe place with limited access and in the storage conditions specified on the supply label.

[figure not shown]
Dosage Schedule:

Boceprevir is administered three times a day using a dosing schedule of 4 capsules every 8 hours. Actual times of dose administration may be modified to fit the patient's schedule, although 7- to 9-hour

intervals between administrations should be maintained. All doses of boceprevir will be given with food (a small snack is sufficient).

Study period and treatment:

All patients will receive an initial 4 weeks of bitherapy with Peg-Interferon and ribavirin (PR).
-If there is a decrease in HCV RNA greater than 1 logarithm with respect to baseline HCV-RNA, the patient will be included in the treatment scheme detailed below.

-If the RNA drop is ≤ 1 log at week 4, PR/boceprevir will be administered for an additional 44 weeks. All cirrhotic patients will receive PR for 4 weeks, followed by RP/boceprevir for another 44 weeks

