8.1 Treatment branches

An open-label, single-arm, multicenter study to evaluate the safety and efficacy of a regimen with boceprevir in polytherapy with peginterferon alfa-2b 1.5 µg/kg or peginterferon alfa-2a 180 µg/kg once weekly subcutaneously (s.c.) and oral ribavirin in adult patients with controlled HIV coinfection in whom prior treatment of chronic hepatitis C with peginterferon and ribavirin has failed.

Since early response to peginterferon (PEG-IFN) and ribavirin (RVB) at week 4 is predictive of response to treatment, either SVR or null response (high negative predictive value: 96%), the duration of response-guided treatment with BOC will depend on the response in ST4, ST8, and ST12.

Patients who achieve a reduction in HCV RNA viral load greater than or equal to one logarithmic unit at week 4 (after the bitherapy phase) will then undergo triple therapy for 32 weeks. If HCV RNA is undetectable at week 8, they will end the tto after 32 weeks of triple therapy and will be followed for another 24 weeks. If HCV RNA is detectable at week 8, at the end of the 32 weeks of triple therapy, patients will receive dual therapy with pegylated interferon and ribavirin for an additional 12 weeks and then follow up for 24 weeks.

Patients who do not achieve a decrease in HCV RNA viral load greater than one logarithmic unit at week 4 after the initial phase of bitherapy (or those who have grade 4 fibrosis - cirrhosis) will receive triple therapy for 44 weeks and will be followed for an additional 24 weeks.

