In addition, a logistic regression analysis will be carried out taking SVR as a dependent variable. The importance of the previously identified prognostic factors will be confirmed by univariate logistic regression. The independence of these factors will then be evaluated using a stepwise method in which the factors that were significant in the univariate analyses will be used.

All analyses will be bilateral and will have a significance level of 5%. The following variables will be analyzed:

Efficacy: sustained virologic response, virologic response at weeks 4, 8, 12, and 24.

Safety: All adverse events, whether or not related to the study medication.

HCV resistance following BOC-containing treatment in patients with virologic failure.

* Predictive factors of SVR: SVR will be analyzed by subgroups according to sex, age, degree of fibrosis at baseline, previous null response, CD4 lymphocyte count at baseline, greater or lesser decrease of one logarithmic unit of HCV RNA at week 4, undetectable HCV RNA at week 8, and pharmacogenetic markers

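### Section 8.1 assigns a non-cirrhotic patient whose week-4 HCV RNA drop is exactly 1 log to both the 32-week and the 44-week regimen, and its first limb contradicts section 4.3

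*Combined protocol and SAP*

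**What the plan says.** The week-4 response after four weeks of peginterferon and ribavirin decides how long boceprevir is given. The rule appears in two places.

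- Section 4.3, first limb: "If there is a decrease in HCV RNA greater than 1 logarithm with respect to baseline HCV-RNA", the patient enters the response-guided scheme. The visible text gives no duration for this group and refers to a scheme that is not reproduced.
- Section 4.3, second limb: "If the RNA drop is ≤ 1 log at week 4, PR/boceprevir will be administered for an additional 44 weeks".
- Section 8.1, first limb: "Patients who achieve a reduction in HCV RNA viral load greater than or equal to one logarithmic unit at week 4" "will then undergo triple therapy for 32 weeks".
- Section 8.1, last paragraph: "Patients who do not achieve a decrease in HCV RNA viral load greater than one logarithmic unit at week 4" receive 44 weeks of triple therapy.

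Cirrhosis overrides the week-4 result. Section 4.3 says "All cirrhotic patients will receive PR for 4 weeks, followed by RP/boceprevir for another 44 weeks", and the last paragraph of section 8.1 likewise sends cirrhotic patients to 44 weeks.

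Section 11.3 lists the week-4 response among the subgroup factors for SVR, as "greater or lesser decrease of one logarithmic unit of HCV RNA at week 4".

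**The concern.** The primary objective is to evaluate response-guided therapy, and week 4 is the first branch of the algorithm. That branch should send every possible result to one regimen only. As written, a result of exactly 1 log satisfies both conditions in section 8.1, so ranking one section above the other does not settle the matter.

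HCV RNA is measured locally at each centre (section 3.7), and no section says how the log drop is to be rounded. Two centres could give different boceprevir durations for the same reported result, and each could point to protocol text in support. It would also be unclear whether such a patient had been treated according to protocol, which matters because section 11.7 removes major deviations from the analysed population.

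**Working it through.** **1. The plan's own figure.** Section 11.2 derives 128 patients from an expected SVR of 60%, a margin of ±8.5 points and a two-sided 95% interval:

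n = 1.96² × 0.60 × 0.40 / 0.085² = 127.6, rounded up to 128.

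This reproduces. It does not depend on the week-4 rule.

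**2. The rules applied at the boundary (non-cirrhotic patient).**

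| Week-4 drop | Section 4.3 | Section 8.1 |
|---|---|---|
| 0.99 log | 44 weeks | 44 weeks |
| 1.00 log | 44 weeks | 32 weeks (first limb) and 44 weeks (last paragraph) |
| 1.01 log | response-guided scheme | 32 weeks |

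The conflict is confined to exactly 1 log. Section 4.3 is consistent within itself. Section 8.1 is not, and its first limb disagrees with section 4.3.

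**3. When the two regimens diverge.** Both start with 4 weeks of dual therapy followed by triple therapy. Up to week 4 + 32 = 36 they are identical. After that the difference in boceprevir is 44 − 32 = 12 weeks. Total treatment also differs (36 against 48 weeks) if week-8 RNA is undetectable. If week-8 RNA is detectable, the 32-week group has 12 more weeks of dual therapy and both end at week 48. Sections 6.6 and 7.3 end treatment for HCV RNA above 100 IU/mL at week 12, for detectable RNA at week 24 and for virological rebound. A patient stopped before week 36 has the same boceprevir exposure on either branch.

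**4. How many patients.** The documents give no distribution for the log drop and no rounding rule, so both are assumptions here. With a normal drop of mean μ and SD σ, and h = 0.005 for two decimals or 0.05 for one decimal:

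P(recorded drop = 1) = Φ((1 + h − μ)/σ) − Φ((1 − h − μ)/σ), multiplied by 128.

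| μ | σ | Two decimals | One decimal |
|---|---|---|---|
| 1.0 | 0.8 | 0.0050, 0.64 patients | 0.0498, 6.4 patients |
| 1.0 | 1.2 | 0.0033, 0.43 | 0.0332, 4.3 |
| 1.5 | 0.8 | 0.0041, 0.53 | 0.0410, 5.2 |
| 1.5 | 1.2 | 0.0030, 0.39 | 0.0305, 3.9 |
| 2.0 | 0.8 | 0.0023, 0.29 | 0.0228, 2.9 |
| 2.0 | 1.2 | 0.0023, 0.30 | 0.0235, 3.0 |

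These counts use all 128 patients and are therefore upper figures. Section 11.2 limits difficult-to-treat patients, including those with cirrhosis, to 30%, so at most 0.30 × 128 = 38 are cirrhotic and at least 90 are not. If the cap were filled by cirrhosis and the same distribution held in the rest, the ranges would shrink by 90/128 to about 0.2 to 0.45 patients at two decimals and 2.0 to 4.5 at one decimal. Withdrawals in the first four weeks reduce them further.

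**5. Effect on the primary result.** The primary estimate is a single pooled proportion. One patient is 1/128 = 0.8 points, against a margin of ±8.5.

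**The case against.** The case for leaving this alone is that it is a drafting slip. All four limbs use 1 log, three of the four agree with each other, and only equality is unsettled. HCV RNA limits elsewhere in the protocol are in IU/mL, so a log drop can be computed without coarse rounding, and exact equality would then almost never occur. This is fair as to size. It does not remove the overlap, and agreement among three limbs does not show which wording the sponsor intended. The scheme missing from section 4.3 cannot help either, since no figure can reconcile two sentences of section 8.1.

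Four stronger readings are tempting and are not supported.

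- A reader might infer two rival algorithms, one per section. The disagreement is at a single value, and part of it lies inside section 8.1.
- A reader might infer that every affected patient's boceprevir duration changes by 12 weeks. That applies only to those still on treatment at week 36.
- A reader might take 3 to 6 patients as the expected count. It requires recording to one decimal, which the documents nowhere state.
- A reader might infer that section 11.3 shuts a patient at 1 log out of the subgroup analysis. Its wording is a label in a list of factors rather than an operational cut-point. It needs aligning with the treatment rule, but it is not a separate contradiction.

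**Conclusion.** The contradiction is real, is in the current text, and should be corrected. It affects non-cirrhotic patients whose reported week-4 drop is exactly 1 log, and it changes boceprevir exposure only for those who reach week 36 on treatment. Its size depends on how the drop is recorded: under the normal assumption above, fewer than 1 of 128 patients at two decimals and about 3 to 6 at one decimal, less cirrhotic patients and early withdrawals.

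A reader might go further and infer that the primary analysis is compromised. The documents do not support this: the sample size of 128 and the ±8.5-point margin stand, and the pooled SVR estimate can barely move at two decimals. What is at stake is uniform assignment across centres at a decision point of the strategy under test, and a clear record of who was treated according to protocol.

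**What to change.** Reconcile section 4.3 and both limbs of section 8.1 to one rule that places every week-4 result in exactly one regimen, with identical wording in any treatment scheme or diagram. State how the log drop is calculated from the two HCV RNA values and to how many decimals, or that it is compared unrounded. Use the same cut-point to define the week-4 subgroup in section 11.3. Which inequality applies is for the sponsor to decide.

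The cost is protocol wording only. Visits, assays, sample size and the primary analysis do not change.

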8.2 Concomitant and rescue medication

Any concomitant medication must be reflected in the CRF in an appropriate way (detailing the product, dosage, route, days of administration, reason for treatment, etc.).

Treatments not allowed:

The administration of treatments that are contraindicated with the study drugs will not be allowed. (see annex technical sheets) and section 10 of the protocol

8.3 Compliance Monitoring

Adherence: to ensure the control and registration of medication, an adherence questionnaire will be added to the data collection notebook. At each visit, the investigator will ask the patient about treatment adherence.

Tablet count: The patient will be asked to bring any leftover medication or empty bottles with them to check whether or not they have taken all the capsules or tablets of the medication since the previous visit.

9. Effectiveness Assessment

9.1 Efficiency parameters

Virological tests to.

Viral RNA

Plasma will be obtained for viral RNA analysis prior to the start of the study and according to the study schedule.

Virological failure shall be defined as described in paragraph 6.1

b. **Methods of Analysis and Sensitivity**

A routine analysis of HIV RNA approved for clinical use will be performed with a lower limit of quantification of 50 copies/mL. The test used on each patient should be the same throughout the trial.

A routine analysis of HCV RNA approved for clinical use will be performed with a lower limit of quantification of 15IU/mL.

10. Safety Rating

10.1 Detection and Recording of Adverse Events

It is the investigator's responsibility to detect and document any event that meets the criteria and definitions of adverse event (AE) or serious adverse event (SAE) as set forth in this protocol. During the study, the existence of adverse events, whether serious or not, will be checked in accordance with the definition given in this section of the protocol.

a) Minimum information to be specified:

Description/definition:

Adverse event (AE) is any adverse health event in a patient or clinical trial subject treated with a medicine, even if it is not necessarily causally related to that treatment. Therefore, it can be any unfavorable and unintended signs (including an abnormal laboratory finding), symptom, or illness temporarily associated with the use of an investigational drug, whether or not related to the investigational drug.

Laboratory abnormalities of clinical importance that meet one or more of the following criteria are also considered AEs:

- It requires additional intervention or treatment.
- Requires a modification of the dose.
- It is accompanied by a clinical manifestation.

Any analytical anomaly that the investigating physician considers to be of clinical importance must be recorded as such in the printed copy of the laboratory report, indicating the physician's initials and the date of revision. An AA is also considered to be any event associated or observed in conjunction with an accidental or intentional overdose of the product, or with abuse or withdrawal of the product.

All AEs will be recorded in the subject's medical record and in the eCRDe. The start and end dates of each AA, the intensity and the relationship with the study drug will be recorded.

The criteria for subject treatment, dose discontinuation, dosage adjustment, withdrawal, or treatment changes will only apply to toxicities attributable to the study drugs (i.e., BOC, PEG-IFN, and RBV).

The classification system for drug toxicity is set out in the DAIDS Table for Grading the Intensity of Adverse Events in Adults and Children, which can be found on the DAIDS RSC website: <http://rsc.techres.com/safetyandpharmacovigilance/>.

In addition, for each AA, the measures taken or the outcome (e.g. hospitalization, discontinuation of treatment) will be recorded.

Adverse reaction (AR) is any harmful, unintended reaction to an investigational drug, regardless of the dose administered. In this case, there is a suspicion of a causal relationship between the investigational drug and the adverse event.

Serious adverse event (SAE) is any adverse event that, at any dose, results in death, threatens the life of the subject, makes hospitalization necessary or prolonged hospitalization, results in permanent or significant disability or disability, or results in a congenital anomaly or malformation. For the purposes of notification, suspected adverse events that are considered medically significant, even if they do not meet the above criteria, will also be treated as serious, including major medical events that require intervention to prevent one of the consequences described above from occurring. Likewise, all suspected transmission of an infectious agent through a drug will be reported as serious. Examples of these events include allergic bronchospasm requiring intensive treatment in an emergency department or at the individual's home, blood dyscrasia or seizures that do not require hospitalization, or the development of drug dependence or abuse.

Medical and scientific judgement should be used to decide whether other situations that have not resulted in the outcomes listed in the above definitions should be reported as SAGs.

A life-threatening term is defined as a situation where, in the opinion of the physician, the patient at the time of the adverse event or adverse reaction is at real risk of death.

Hospitalization or prolongation of a hospitalization is a criterion for considering an AA to be serious. Only admission in which the patient spends the night in the hospital should be considered as hospitalization. The following situations will not meet the AAG criteria:

- if hospitalization or prolongation of hospitalization is necessary to perform a procedure required by the protocol (for example, if day or night visits will be made for biopsies or surgeries required by the protocol).
- if hospitalization or prolongation of hospitalization is part of the facility's routine procedure (e.g., removal of a stent after surgery)
- in case of scheduled hospitalization for a pre-existing process that has not worsened (e.g. scheduled hospitalization for the implantation of a knee prosthesis for a previous osteoarthritis process)

Grade IV laboratory alterations will be considered AAG.

DO NOT confuse the concept of "serious" with "severe" which refers to the intensity of the adverse event or adverse reaction.

Unexpected serious adverse reaction (RAGI) is a serious adverse reaction whose nature or severity does not correspond to the information regarding the product (for example, the investigator's manual in the case of an investigational medicinal product not authorised for marketing or the product label in the case of an authorised medicinal product).

b) Imputability criteria.

The causal relationship between the investigational product and the occurrence of AA/AAG shall be established on the basis of clinical judgment. To this end, other causes will be considered and studied, such as the natural history of the underlying diseases, concomitant treatment, other risk factors and the temporal relationship of the event with the investigational product. In addition, the technical data sheet of the products will be consulted.

In order to analyse the possible cause-effect relationship, the temporal relationship between the administration of the drug and the AA, possible alternative causes, the evolution (complete remission,

partial recovery, death, sequelae, persistence), persistence or not after the suspension of administration, reappearance with the readministration of the product or the prior knowledge of said event coinciding with the known or expected response pattern of the drug under study will be considered.

The causal relationship of an AA with the medication under study will be established according to the following definitions:

Unlikely relationship: The adverse event does not occur after a plausible chronological sequence related to the administration of the product under study and/or is reasonably explainable by other factors, such as the patient's clinical status or other concomitant therapeutic, toxic, or environmental interventions. In addition, it does not match the known or expected response pattern of the drug.

Possible relationship: the adverse event occurs after a plausible chronological sequence related to the administration of the product under study, but can also be explained by the patient's clinical status or other concomitant therapeutic, toxic, or environmental interventions. It also matches the known or expected response pattern of the drug.

Probable relationship: The adverse event occurs after a plausible chronological sequence related to the administration of the product under study, cannot be reasonably explained by the patient's clinical status or other concomitant therapeutic, toxic, or environmental interventions, and after withdrawal or reduction of the dose of the suspect drug the event follows a logical clinical sequence. It also matches the known or expected response pattern of the drug.

Very likely relationship: the adverse event occurs after a plausible chronological sequence related to the administration of the product under study, cannot be reasonably explained by the clinical status of the patient or other concomitant therapeutic, toxic or environmental interventions, after withdrawal or reduction of the dose of the suspect drug the event follows a logical clinical sequence and it is necessary that after the readministration of the suspicious drug the adverse event reappears. It also matches the known or expected response pattern of the drug.

Unrelated: Adverse event clearly due to causes unrelated to the medication under study and the criteria for another causal relationship are not met.

Non-assessable relationship: any notification that suggests an adverse effect, which cannot be judged because the information is insufficient or contradictory and which cannot be supplemented or verified.

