4.1 Identification of the investigational medicinal product

Generic name: Boceprevir

Trade name: Victrelis®

Composition: boceprevir 200 mg.

Pharmaceutical form: hard gelatin capsules.

Generic name: Peginterferon (alpha-2b or alpha-2a)

Trade name: Pegintron® or Pegasys®

Composition: peginterferon alfa-2b 80-150mcg or peginterferon alfa-2a: 180 micrograms

Pharmaceutical form: solution for injection

Generic name: Ribavirin Trade name:

Ribavirin Teva®.

Composition: ribavirin: 200 mg

Dosage form: hard capsule

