6.3 Guidelines for BOC Dose Modification

The dose of BOC cannot be reduced in the study.

Grade 1 and 2 AEs require close follow-up but no change in treatment.

All grade 3 toxicities will be treated by the facility investigator as appropriate. Any grade 4 toxicity that, in the opinion of the centre's investigator, is directly related to BOC, will be treated with the permanent suspension of the latter.

In case of intolerance to the BOC, its administration will be suspended; The dose cannot be reduced. If BOC is temporarily or permanently stopped, patients may continue to receive PEG-IFN and RVB.

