6.4 Trial treatments

DRUG SUPPLY AND LABELLING

In this study, 2 drugs already on the market and authorized for use in HIV-HCV co-infected patients will be used; peginterferon and ribavirin; The study drug, boceprevir, will be provided by MSD throughout the study and distributed by the Coordinating Center. For clinical trials carried out in Spain, relabelling in Spanish is mandatory.

See section 4.3

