- Dose delay of 3 to 5 days: Giving subsequent doses every 5 to 6 days until the patient gets back to their original schedule (for example, if Monday is the usual day of administration and the dose is delayed until Saturday, the next dose will be given on Thursday, the next dose on Tuesday, and the next dose on Monday).
- 6-day dose delay: discontinue that week's dose and continue with the usual schedule the following week (e.g. if Monday is the usual day of administration but the dose is delayed until the following Sunday, the dose is considered to have been interrupted and the next injection will coincide with the following week's dose, on Monday).
- Dose delay of 7 or more days: The investigator may resume administration of the study drug at any time up to 28 days after the last dose and, if necessary, administer the dose every 5 or 6 days until the weekly dose is received on the patient's usual scheduled day.

Treating the Side Effects of RBV

The most common AA in RBV treatment is anemia, which may be due to hemolysis or decreased release of red blood cells from the bone marrow. Anemia usually appears 1 to 2 weeks after you start receiving RBV and usually goes away within 4 to 8 weeks of withdrawal or reduction of the drug's dose. In patients with anemia secondary to RBV-induced hemolysis, an elevation of indirect bilirubin is common. BOC may increase the incidence or severity of anemia. In case of anaemia during treatment with BOC and RBV, the dose adjustment of RBV, as described below, takes precedence over BOC.

NOTE: A serious side effect of RBV is its teratogenicity; therefore, it is recommended not to administer RBV to pregnant or breastfeeding women and to men whose partner is pregnant. Women who become pregnant during the study will be required to discontinue study treatment and undergo withdrawal assessments.

The dose of RBV in this study will depend on weight at study entry (see section 5). The following table shows the recommendations for dose reduction in case of anemia. The administration of epoetin (EPO) will be at the discretion of the centre's researcher. If the administration of RBV is temporarily or permanently stopped, patients may continue to receive PEG-IFN and BOC.

Board. Recommended RBV dose reduction in anaemia

	Starting dose	Measure
--	---------------	---------

Hemoglobin <10 g/dL, ≥8.0 g/dL.	1,400 mg/day 1,200 mg/day	Decrease RBV to 1,000 mg/day
	1,000 mg/day	Decrease RBV to 800 mg/day

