11.3 Analysis

In this open study, all variables will be tabulated. Quantitative variables will be described by the number of available and omitted observations, the mean, the median, the standard deviation, the interval (minimum and maximum) and the first and third quartiles. Of the qualitative variables, the frequency and percentage will be presented. Omitted values will be tabulated with their frequency, but will not be included in the calculation of the percentages.

The primary endpoint will be assessed with a bilateral CI of 95% around the observed proportion of SVR. The analysis of the primary endpoint in SVR will be carried out in two ways. Patients who withdrew from the study within the first four weeks will be included in the main analysis, which will be counted as SVR failures. As a secondary analysis, an SVR analysis will also be performed, but restricted to patients who have not withdrawn from the study in the bitherapy period in the first four weeks. In both analyses, patients in whom SVR data are lacking due to premature withdrawal from the study at any time after the initial bitherapy period of the first four weeks will be included and counted as SVR failures.

Inferential analysis of boceprevir efficacy will be assessed by SVR at week 24 and the 95% confidence interval. A similar analysis will be applied to evaluate the secondary variables. For continuous quantitative variables, the mean or median and the 95% confidence interval or the interquartile interval shall be calculated.

Descriptive analyses of treatment-occurring adverse events and treatment-occurring adverse events that are possibly or likely related to the study drug will be performed. With regard to the safety assessment in the AEs, the 95% CI of the percentage of grade 3 or higher adverse events and other serious adverse events reported by the centres shall be provided. The highest grade episode per person over time will be used. Descriptive tables will be provided summarizing the events and the number of people who have presented the events by grade.

Variations in HIV-1 viral load or RNA and CD4+ T cell count at each post-enrollment visit will be summarized. The rates and reasons for premature discontinuation of treatment, including HCV treatment failures, will be summarized.

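### Adverse events carry one causality rating to an inconsistently defined *study drug*, so the related-event summary in section 11.3 has no single meaning

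*Combined protocol and SAP*

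**What the plan says.** Section 10.1 states what is recorded for each adverse event: "The start and end dates of each AA, the intensity and the relationship with the study drug will be recorded". The causality scale later in 10.1 also rates one object: "The causal relationship of an AA with the medication under study will be established according to the following definitions". None of the supplied text asks for a rating drug by drug.

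The name of the rated object changes from place to place:

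- Section 6.4 equates it with boceprevir: "The study drug, boceprevir, will be provided by MSD throughout the study". Section 1.8, on study drug information, also names boceprevir alone.
- In 10.1, shortly after the recording sentence, the criteria for dose changes and withdrawal "will only apply to toxicities attributable to the study drugs (i.e., BOC, PEG-IFN, and RBV"), which is the whole regimen.
- In 10.3, under missed or deferred peginterferon doses, the singular term refers to peginterferon: "The investigator may resume administration of the study drug at any time up to 28 days after the last dose".
- The section headed "4.1 Identification of the investigational medicinal product" lists boceprevir, peginterferon and ribavirin together.

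The analysis text in 11.3 uses the singular term without defining it. Of the descriptive analyses it announces, one concerns "treatment-occurring adverse events that are possibly or likely related to the study drug will be performed".

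**The concern.** Safety is part of the primary objective (section 5), and section 8.1 describes a single-arm study. With no control group, investigator attribution is the only planned summary that bears on which drug caused an event. Section 10.3 says that the events seen with boceprevir regimens mostly mirror those of the peginterferon/ribavirin backbone, so overlapping toxicity is to be expected.

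The ambiguity reaches the rater directly. Section 10.1 asks investigators to weigh concomitant treatment as an alternative cause. It does not say whether the backbone is such a treatment or part of the product being rated. Two investigators could rate the same event differently and both comply with the text. A reader of the final report could not tell whether the related-event percentage describes boceprevir or the combination.

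**Working it through.** The plan gives no figure on this point. Its one design figure does reproduce: 1.96² × 0.60 × 0.40 / 0.085² = 127.6, rounded up to 128 (section 11.2). It does not depend on how causality is recorded.

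**Step 1. Can usage elsewhere settle the meaning?** One could try the rule that the singular always means boceprevir and the plural means all three drugs. Sections 1.8, 6.4 and 10.1 fit that rule. The peginterferon missed-dose text in 10.3 breaks it, because there the singular is peginterferon. Section 4.1 also places all three drugs under one investigational-product heading. No other section resolves the matter.

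**Step 2. What does each reading deliver?** Let *a* be the percentage of patients with at least one event related to boceprevir. Let *b* be the percentage with at least one event related to any of the three drugs. Boceprevir is one of the three, so *b* ≥ *a*. The difference *b* − *a* is the percentage of patients whose related events are all attributed to the backbone alone.

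- Boceprevir reading: the table in 11.3 gives *a*. Backbone causality is not recorded, so *b* is not available.
- Regimen reading: the table gives *b*. During triple therapy the rating does not identify boceprevir-related events, so *a* is not available.
- Mixed reading: suppose a fraction *s* of patients is at sites using the boceprevir reading, and *a* and *b* are the same at all sites (an assumption). The pooled result is *s*·*a* + (1 − *s*)·*b* = *b* − *s*·(*b* − *a*). That equals neither quantity unless *s* is 0 or 1, or *a* = *b*.

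**Step 3. For how much of treatment is the rating needed?** From 4.3 and 8.1, every patient has 4 weeks of peginterferon and ribavirin before boceprevir starts. Events with onset in those weeks can be assigned to the backbone by date. The planned triple-therapy share of treatment is then:

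- week-4 response and undetectable at week 8: 32 / (4 + 32) = 32/36 = 89%;
- week-4 response but detectable at week 8: 32 / (4 + 32 + 12) = 32/48 = 67%;
- insufficient week-4 response, or cirrhosis: 44 / (4 + 44) = 44/48 = 92%.

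These are shares of planned treatment time, not of events.

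**Step 4. Which results use the rating?** In 11.3 it feeds the related-event descriptive analysis. The confidence intervals planned for grade 3 or higher and serious events carry no relatedness condition, and the safety variable in 11.3 covers every adverse event regardless of causality. Neither uses the rating.

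**The case against.** The strongest reply is that little of the safety analysis is touched. The objective concerns boceprevir in combination, no section commits to separating toxicity by drug, and the main safety results are all-cause. This stands and limits the point to one descriptive summary.

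It can also be said that 10.1 presents its list as minimum information. The case-report variables are in Annex VI, which is not in the supplied text and may already hold per-drug fields. This cannot be excluded. If it is so, the fields are in place, but 10.1 and 11.3 still need to say which rating is analysed.

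A reader might infer that boceprevir toxicity cannot be isolated under any reading. The documents do not support that: under the boceprevir reading the 11.3 table is the boceprevir-related result, and onset dates separate the lead-in events.

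A reader might also infer that the dose and stopping rules cannot operate without a database code. Section 6.3 requires the investigator's opinion that a grade 4 toxicity "is directly related to BOC, will be treated with the permanent suspension of the latter". That opinion can be formed at the bedside, and the haematology tables in 10.3 act on laboratory thresholds. What remains is that the terms in those rules and the recorded rating are not aligned.

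Finally, per-drug ratings are clinical judgement under overlapping toxicity and cannot stand in for a control arm. That is correct, but it does not justify leaving the rated object undefined.

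**Conclusion.** The point holds as a defect of definition and data capture. The supplied text records one rating against a term with three uses, and the related-event result in 11.3 can mean *a*, *b* or a mixture. The consequence is confined to that descriptive summary. All-cause results and the intervals for grade 3 or higher and serious events are unaffected, and lead-in events remain assignable by onset date, although 11.3 plans no such analysis.

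The numerical size is unknown. The gap is zero if every patient with any related event also has a boceprevir-related one, and it grows with the share of patients whose related events are backbone-only. A reader might assume that share, say 20% to 50%, and conclude that the result moves by 20 to 50 points, well beyond sampling error. That only restates the assumption, since the documents give no related-event rate. Comparison with a confidence-interval width is also misplaced, because 11.3 plans the related-event analysis as descriptive.

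The conclusion assumes that Annex VI does not already provide per-drug fields. The statement about mixed quantities further assumes that sites do read the term differently, which the documents permit but do not show. The change is still worthwhile before data collection, because attribution by drug is hard to reconstruct reliably afterwards.

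**What to change.** 1. Define *study drug* once and use it consistently in 10.1, 10.3 and 11.3. State whether peginterferon and ribavirin count as concomitant treatment when causality is judged.
2. In 10.1 and the eCRF, record the relationship separately for boceprevir, peginterferon and ribavirin, unless Annex VI already does so.
3. In 11.3, report the percentage of patients with events related to boceprevir and the percentage with events related to any of the three drugs, and name the rating behind each.
4. Reconcile the discontinuation passages that refer to the study drug (6.6 and 7.3) or to boceprevir-related toxicity (6.3 and 10.3) with the definition. This is a matter of consistent terms; no clinical rule is proposed here.

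The cost is two more eCRF fields per event, one more table and a small data-entry burden. The sample size does not change.
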